3.3 Visit Structure

The visit structure and scheduled assessments are detailed in Table 6-1: Schedule of visits, of the protocol.

3.4 Sample Size

The study will include up to 16 patients; approximately 4-6 patients in Part I and up to 10 patients in Part II if sponsor decision to initiate such. As this is an exploratory study, no formal samples size calculation has been performed. However, it is estimated that a sample size of 6 patients in each group (monotherapy and combined treatment) is sufficient to explore the potential effect of TG02 to induce immune responses and to assess safety in the induction phase.

3.5 Changes from the Protocol Planned Analysis

The efficacy analysis set is defined in Section 11.3 of the protocol and includes all patients who undergo surgery after the treatment period. This analysis set has been modified to include patients from whom a biopsy is obtained at the time of surgery, for patients who do not proceed to surgery.

4 STUDY PATIENTS

The tables will present the two treatment groups for both parts of the study side-by-side as 'Part I (TG02)' and 'Part II (TG02 + Checkpoint Inhibitor (CPI))'.

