TG02-treatment and DTH testing will occur in an identical manner to that described for the Part I of the study. Pembrolizumab should be administered as described previously. During the course of the study, the patient can expect to receive 2-4 intravenous infusions; week 4, week 6, and week 8 if surgery takes place Day51-63/Week8-10, and week 10 if surgery is delayed after day 64/Week 10. The dosing regimen should be the same for all patients at all sites.

Baseline and screening assessments:

Demographic details, medical and medication history, physical examination, vital signs (blood pressure, heart rate, tympanic temperature, weight, height), 12-lead ECG, ECOG performance status, routine laboratory testing (haematology and clinical chemistry), PET-CT, tumour biopsy, collection of blood for immune activity (PBMCs, serum and whole blood) and CEA.

Efficacy assessments:

- TG02-specific DTH response
- Presence of TG02 specific T-cells
- Change in intra-tumoural lymphocytes

- Change in immunological and pathological markers in tumour tissue
- Changes in FDG PET-CT images e.g. change in standard uptake value (SUV)
- Changes in CEA from baseline throughout treatment
- Changes in circulating tumour cells and/or circulating tumour DNA
- Functionality of RAS mutation specific T cells in tumour tissue and peripheral blood

Safety assessments:

Safety will be assessed by incidence and severity of adverse events as per NCI Criteria for Adverse Events (CTCAE) (v4.03: June 14, 2010), and by changes from baseline in laboratory variables, physical examination, vital signs and ECOG performance status.

Statistics:

The results from this study will be presented using descriptive statistical methods. Data will be presented by time of measurement, e.g. at baseline, week 1, week 4, week 8 etc. In general, continuous variables will be described using standard summary statistics such as number of observations, mean value, standard deviation, minimum and maximum value, median, and first and third quartiles. Categorical variables will be summarised in frequency tables as counts and percentages. All individual data collected will be presented in data listings. Patients screened but not included in the study will not be presented in any tables or listings.

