4.8. Rationale for dose regimen

TG02

TG02 given in the TG02-treatment will be administered to the patient at week 1, 2, 3, 4, and 6. If surgery is scheduled after week 10 one more TG02-treatment will be given in week 10. In addition to this TG02 will at certain time points (week 1, week 4, week 6, week 8 and possible week 10), be administered intradermally (without prior administration of GM-CSF) as a DTH test to evaluate the immunological response. The rationale for this regimen is based on the results from the previous and ongoing studies with TG01/GM-CSF that demonstrate that prevailing RAS mutation specific T cells responses are induced in cancer patients after 4-6 weeks of vaccination.

Pembrolizumab

Although the licensed dosing regimen for pembrolizumab is 3-weekly, in this window of opportunity study there is limited time between the start of TG02 vaccinations and surgery. Also, in order that the scheduling of study visits can be minimised to avoid extra patient visits, it is proposed to administer the pembrolizumab 2-weekly. Based on the data reported from the KEYNOTE 006 study for melanoma (Schachter 2017), the efficacy was similar between the 2-weekly and 3-weekly schedule with very similar safety profiles. Additionally, time needs to be allowed for a TG02 specific immune response to be induced; therefore, pembrolizumab will be started at week 4 and continued two-weekly until surgery

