The treatment period will be from Day 1 (Week 1) and up to surgery, which is planned for week 8 but can occur in a window up to week 14. The following assessments will be performed on Day 1, Day 8, Day 15, Day 22, Day 36, Day 50 and if surgery is after week 10 (Day 64):

- Vital signs (heart rate, blood pressure and tympanic body temperature) and ECOG performance status
- Concomitant medications and adverse events will be monitored continuously
- Physical examination, haematology and serum biochemistry (Table 9-1) before treatment (Day 1) and during treatment on Day 15, Day 36, Day 50 and if surgery after week 10 (Day 64).
- TG02 treatment will be administered on Days 1, 8, 15, 22 and 36. If surgery after week 10 TG02 treatment will also be given at week 10 (Day 64).
- Pembrolizumab will be given on Days 22 and 36. If surgery is scheduled after Day 50/Week 8, pembrolizumab will be given at Day 50/Week 8. If surgery scheduled after Day 64/Week 10, a further pembrolizumab infusion will be given at Day 64/Week 10.
- DTH tests will be performed at baseline (Day 1), week 4 (Day 22), week 6 (Day 36) and week 8 (Day 50) (if surgery is scheduled for week 8 the DTH test should be performed two days before surgery). If surgery is after week 10, and the patient has had negative DTH tests up to and including week 8, an additional DTH test should be performed at week 10 (Day 64).

- Blood samples for in vitro assessment of TG02-specific immune responses (Immunology sample, PBMC) will be taken at baseline (Day 1) and Day 50. If surgery is after week 10, an additional sample should be taken as close as possible up to the date of surgery (see separate Immune monitoring plan).
- The CEA biomarker will be evaluated at Day 50. If surgery is after week 10 a third sample will be taken at Day 64 or just prior to surgery, whichever is the more appropriate.
- Tumour samples for assessment of immune response will be taken at time of surgery. If for any reason the patient will not have surgery a biopsy will be obtained if possible at the latest by week 14 (see separate Immune monitoring plan).
- FDG PET-CT scan for tumour assessment of standard uptake value (SUV-max) as close as possible up to date of surgery.
- Circulating Tumour Cells (CTC) will be evaluated at Day 1 and Day 50. If surgery is after week 10, an additional sample can be taken as close as possible up to the date of surgery.

Additional monitoring during the first 2 hours after any TG02-treatment:

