4.2 Analysis Sets

The **Safety Analysis Set (SAF)** comprises all patients who receive any amount of TG02/GM-CSF and/or pembrolizumab. This analysis set will be applied for demographic, baseline and safety data.

The **Efficacy Analysis Set (EAS)** comprises all patients who undergo surgery after the treatment period or patients from whom a biopsy was obtained at the time of planned surgery (for patients who do not proceed to surgery). This analysis set will be applied for demography, baseline and efficacy data.

The **Per Protocol Analysis Set (PPAS)** is a subset of the EAS but patients with major protocol deviations are excluded. The analysis set will be applied for efficacy data.

The list of patients to be included in each of the analysis sets is to be agreed between the study statistician and the sponsor prior to database lock, once all study data are available.

All enrolled patients will be listed indicating their membership to each analysis set together with the reason for exclusion.

All listings will be based on all enrolled patients separately for Part I and Part II unless specified otherwise.

The outputs will be reported using the following analysis sets:

Output	SAF	EAS	PPAS
Demography	x	x	
Medical History	x	x	
Details of Previous Cancer Treatment (Before/After + up to First IMP)	x	x	
Concomitant Medications	x	x	
Administrations (Patient + Visit Level)	x	x	
Standard Uptake Value (kBq/mL) Values and Change from Baseline over Time		x	x
Carcinoembryonic Antigen (ug/L) Values and Change from Baseline over Time		x	x

Immune Response		×	×
DTH Skin Test Reactions		×	×
T-cell Responders / Biopsy / Cytokines / ctDNA		×	×
AE / Labs / Vitals / ECOG	×		
Listings + Figures	×		

If any of the analysis sets overlap (e.g. SAF = EAS) the outputs will not be repeated.

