5.2 Adverse Events

Any events that are unequivocally due to progression of disease will not be reported as AEs or SAEs.

Adverse events will be coded according to the latest MedDRA dictionary version.

A treatment-emergent adverse event (TEAE) is defined as an AE with start date/time on or after the first administration of IMP. A pre-treatment AE is defined as an AE with start date/time prior to the first administration of IMP.

There will be no imputation of unknown dates for the calculation of duration or study day. However, for sorting and assignment, if the start date is unknown then it will be assumed to be treatment emergent unless the partial start date or other data (i.e. stop date) indicates differently.

Assessment of AE severity will be based on the NCI CTCAE which includes five grades, with grade 5 being death. If the severity of an event changes during the course of that event, only the maximum severity/grade will be summarised in the tables.

The relationship to each IMP (TG02, GM-CSF, pembrolizumab) is assessed as not related or related.

An overview summary table will summarise the number of events and the number and percentage of patients with at least one of the following TEAEs:

- total TEAEs
- total serious TEAEs
- total IMP related serious TEAEs
- TEAEs leading to TG02 and GM-CSF withdrawal
- TEAEs leading to pembrolizumab withdrawal
- TEAEs leading to study withdrawal
- TEAEs leading to death
- TEAEs by severity

- TEAEs by relationship to each IMP (related, not related) separately
- SAEs by relationship to each IMP separately

The number of events and the number and percentage of patients experiencing TEAEs will be presented by SOC and PT for the following TEAEs:

- Total TEAEs: If a patient experienced more than one TEAE, the patient will be counted once for each SOC and once for each PT. This summary will be repeated for serious TEAEs only.
- Total TEAEs by severity: If a patient experienced more than one TEAE, the patient will be counted once for each severity experienced during the study.
- TEAEs by relationship to each IMP: If a patient experienced more than one TEAE, the patient will be counted once for each SOC and once for each PT at the closest relationship to study drug. This summary will be repeated for serious TEAEs only.

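### Part II adverse event tables count events before the first pembrolizumab infusion, and any never-infused patient, as combination experience

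*SAP*

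**What the plan says.** - **Columns.** SAP section 4: "The tables will present the two treatment groups for both parts of the study side-by-side as" one column per part. The second is headed "Part II (TG02 + Checkpoint Inhibitor (CPI", closing brackets omitted here.
- **Population.** Under SAP 4.2 the Safety Analysis Set "comprises all patients who receive any amount of TG02/GM-CSF and/or pembrolizumab". No infusion is needed to enter the Part II column.
- **Event window.** SAP 5.2: "A treatment-emergent adverse event (TEAE) is defined as an AE with start date/time on or after the first administration of IMP". In Part II the first such product is TG02/GM-CSF on Day 1.
- **Pembrolizumab timing.** Protocol 6.4.2: "Pembrolizumab will be given on Days 22 and 36", with later infusions depending on the surgery date. The delay is deliberate. Protocol 4.8 wants time for an immune response to TG02, so "pembrolizumab will be started at week 4 and continued two-weekly until surgery".
- **TG02 timing.** Protocol 6.4.2: "TG02 treatment will be administered on Days 1, 8, 15, 22 and 36", plus Day 64 if surgery falls after week 10. The Protocol synopsis says of Part II: "TG02-treatment and DTH testing will occur in an identical manner to that described for the Part I of the study".
- **Denominator.** SAP 6.4.2 uses all patients in the analysis set, except in tables by time point. Protocol 7.6 keeps the safety data of patients who withdraw before surgery.
- **Objective.** SAP 3.1 states the Part II primary safety objective as the safety of TG02-treatment together with pembrolizumab.

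**The concern.** Together these rules give Part II a single AE column named for the combination, in which the first three weeks are TG02/GM-CSF alone. A Day 10 event is printed as a combination event although the patient has had no pembrolizumab. A patient who stops before Day 22 sits in the denominator of every Part II AE percentage, including the rows for pembrolizumab-related events and for events leading to pembrolizumab withdrawal.

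The tables affected are total, serious, by-severity, by-relationship and fatal TEAEs. What is at stake is the quantity that the SAP's Part II objective asks for: how often events occur once patients are on both treatments. The planned tables do not give it. With at most 10 patients planned, one misplaced patient moves a rate by about 10 percentage points.

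**Working it through.** The plan states no event rate, sample-size calculation or test, so there is no figure of its own to reproduce. The checks below size the effect.

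**1. Calendar.** Week w begins on Day 7(w - 1) + 1. Week 4 is Day 22, week 6 Day 36, week 8 Day 50 and week 10 Day 64, in agreement with Protocol Table 6-1.

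**2. Share of pre-surgery time on TG02 alone.** The formula is 21 / (surgery day - 1). The surgery days come from the window in Table 6-1.
- Day 50: 21/49 = 42.9%
- Day 64: 21/63 = 33.3%
- Day 92: 21/91 = 23.1%

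Protocol 9.2.1.2 collects AEs for 28 days after the final treatment. Taking the last scheduled dose as Day 36, 50 or 64, the elapsed time to the end of that window is 63, 77 or 91 days:
- 21/63 = 33.3%
- 21/77 = 27.3%
- 21/91 = 23.1%

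These are shares of time. The share of events could be larger or smaller.

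**3. Share of vaccinations.** Days 1, 8 and 15 precede the first infusion: 3 of 5 (60%), or 3 of 6 (50%) if the Day 64 dose is given.

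**4. Effect on a printed percentage.** The counts are assumed, with 10 Part II patients.
- *Overstatement.* Three patients have an event after the first infusion, two others only before it, and one patient is never infused. The planned table prints (3 + 2)/10 = 50%. The combination-period rate is 3/(10 - 1) = 33.3%.
- *Understatement.* Three patients have an event after the first infusion and nobody has one only before it. The table prints 3/10 = 30%. The combination-period rate is 3/9 = 33.3% with one patient never infused, or 3/8 = 37.5% with two.
- *No early-only events and everyone infused.* Both give 3/10 = 30%, and the discrepancy vanishes.

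**5. How likely a never-infused patient is.** The documents give no rate of stopping before Day 22. If the chance per patient is d, the chance of at least one in 10 is 1 - (1 - d)^10: 18% for d = 2%, 40% for d = 5% and 65% for d = 10%. The values of d are assumptions.

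**6. What the other planned tables recover.** SAP 5.2 tabulates TEAEs by relationship to each product, including TG02/GM-CSF only and pembrolizumab only. This leaves unrelated events unsplit, and it does not separate a TG02-related event on Day 10 from one on Day 30. Laboratory and vital-sign summaries (SAP 5.3, 5.4) and ECOG tables (SAP 5.6) are by visit, so visits before Day 22 can be identified there.

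**The case against.** The strongest reply is that the column names an assigned regimen. Part II is a planned sequence with a deliberate pembrolizumab start at week 4, and counting from the first dose of any product gives both parts the same origin. That stands, and it is the reason to keep the from-Day-1 table. It does not supply a combination-period rate, and the SAP does not say that the heading means assigned regimen rather than exposure.

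A second reply is that all TEAEs and all product administrations are listed, and SAP 5.1 summarises the number of pembrolizumab doses. Readers could then date each event against the first infusion and find anyone never infused. That is true with about 10 patients, and the study is descriptive with no hypothesis. But a split made later from listings would be unplanned. The table shells are a separate document and might already contain one; the SAP text does not.

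Some stronger inferences are tempting but not supported:
- *A reader might infer that attribution ignores timing.* Protocol Appendix II lists receipt of the suspect drug and a reasonable temporal relationship first among its causality factors. An event before Day 22 should not be rated pembrolizumab-related, so the by-relationship tables are partly protected in the numerator.
- *A reader might infer that every Part II safety table is affected.* The by-visit tables are not materially affected, and a second laboratory baseline is not needed.
- *A reader might infer that pooling gives 16 patients of TG02-alone data.* With zero events, the one-sided 95% upper limit would then fall from 1 - 0.05^(1/6) = 39% to 1 - 0.05^(1/16) = 17%. But Part II supplies only 21 days and three vaccinations per patient, against five or six vaccinations in Part I. The lower figure could apply only to events on Days 1-21, and it assumes full enrolment of 6 and 10.
- *A reader might infer that the Safety Steering Committee's decisions are compromised.* Its staggered review uses data from the first three patients, not these final tables.

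**Conclusion.** The point holds for the Part II AE tables. Events before the first infusion, and any patient never infused, are reported as combination experience, and no rule in the SAP separates them. The TG02-only period is 23% to 43% of pre-surgery time, or 23% to 33% of the AE collection window on the dosing assumptions above. The bias has no fixed sign: early-only events raise the printed rate, and never-infused patients lower it.

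The size in any one table rests on assumed counts. Never-infused patients are possible under the definitions but are not a known number; if there are none, only the timing problem remains. This is a reporting gap on a primary safety objective in a small descriptive study. It does not invalidate the analysis, and it is cheap to close.

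**What to change.** In SAP 5.2:
1. Keep the from-Day-1 tables and label them as a summary of the assigned regimen.
2. For Part II, add the TEAE overview and the SOC/PT tables split by onset before versus on or after the first pembrolizumab infusion. Events in never-infused patients stay in the first group. State a rule for missing onset dates or times, in line with the existing treatment-emergent rule.
3. Use patients with at least one infusion as the denominator for the post-infusion tables and for the pembrolizumab-related and pembrolizumab-withdrawal rows.
4. State the number of Part II patients never infused.
5. Show Part I split at Day 22 alongside, so that like is compared with like.
6. If a pooled TG02-alone summary is wanted, limit it to Days 1-21 in both parts.

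This uses event and administration dates already in the plan and changes nothing in dosing, visits or data collection. SAP section 1 already provides for revision before database lock. The cost is some programming, a few more columns and slightly smaller denominators. The post-infusion columns also describe only patients who reached an infusion, and a footnote should say so.

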4.1 Disposition of Patients

The number and percentage of all patients enrolled and included in the efficacy analysis set, per protocol analysis set and safety analysis set, who completed the study and prematurely withdrew (including a breakdown of the primary reason for withdrawal) will be presented.

4.2 Analysis Sets

The **Safety Analysis Set (SAF)** comprises all patients who receive any amount of TG02/GM-CSF and/or pembrolizumab. This analysis set will be applied for demographic, baseline and safety data.

The **Efficacy Analysis Set (EAS)** comprises all patients who undergo surgery after the treatment period or patients from whom a biopsy was obtained at the time of planned surgery (for patients who do not proceed to surgery). This analysis set will be applied for demography, baseline and efficacy data.

The **Per Protocol Analysis Set (PPAS)** is a subset of the EAS but patients with major protocol deviations are excluded. The analysis set will be applied for efficacy data.

The list of patients to be included in each of the analysis sets is to be agreed between the study statistician and the sponsor prior to database lock, once all study data are available.

All enrolled patients will be listed indicating their membership to each analysis set together with the reason for exclusion.

All listings will be based on all enrolled patients separately for Part I and Part II unless specified otherwise.

The outputs will be reported using the following analysis sets:

Output	SAF	EAS	PPAS
Demography	x	x	
Medical History	x	x	
Details of Previous Cancer Treatment (Before/After + up to First IMP)	x	x	
Concomitant Medications	x	x	
Administrations (Patient + Visit Level)	x	x	
Standard Uptake Value (kBq/mL) Values and Change from Baseline over Time		x	x
Carcinoembryonic Antigen (ug/L) Values and Change from Baseline over Time		x	x

Immune Response		×	×
DTH Skin Test Reactions		×	×
T-cell Responders / Biopsy / Cytokines / ctDNA		×	×
AE / Labs / Vitals / ECOG	×		
Listings + Figures	×		

If any of the analysis sets overlap (e.g. SAF = EAS) the outputs will not be repeated.

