7.5. Discontinuation Criteria

Patient Withdrawal

Single patient termination is by definition when the patient is withdrawn or when the patient has died or completed the study. The study termination page in the eCRF must be completed.

In accordance with the Declaration of Helsinki, each patient is free to withdraw from the study at any time without giving their reason(s).

The investigator also has the right to withdraw patients from the study in the event of:

- withdrawal of the patient's consent
- surgery does not proceed and the patient is unable or unwilling to provide a biopsy at the time of cancelled surgery
- occurrence of an exclusion criterion which is clinically relevant and affects the patient's safety, and discontinuation is considered necessary by the Investigators and/or Targovax.
- therapeutic failure requiring urgent additional medication (if applicable)
- occurrence of AEs, if discontinuation of trial medication is desired or considered necessary by the Investigator and/or patient (if applicable)
- intake of non-permitted concomitant medication where the predefined consequence is withdrawal from the trial
- patient non-compliance with study procedures/requirements
- major protocol violation which potentially impacts the study endpoints

Study Termination

The whole study may be discontinued at the discretion of the Investigator or Sponsor in the event of any of the following:

- Occurrence of AEs not seen previously which by virtue of their nature, severity and duration are considered to necessitate study termination; OR the unexpected incidence of known AEs
- Medical or ethical reasons affecting the continued performance of the study
- Difficulties in the recruitment of patients
- Cancellation of the drug development as such or for the given indication

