7.6. Replacement Policy

If a patient during the treatment period before surgery is withdrawn, the patient will be considered to be replaced. All safety data collected will remain part of the safety analysis.

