6 EFFICACY EVALUATION

All efficacy evaluations will be performed on the efficacy and per protocol analysis sets unless specified otherwise.

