6.1 Primary Immune Endpoints

A systemic immune response is defined as having a positive in vivo DTH and/or a positive in vitro T-cell response at least once during the study. Change in intra-tumoural T-cells in resected tumour tissue at surgery compared to pre-TG02-treatment core biopsy will be investigated.

The systemic immune responses are assessed by:

- TG02-specific DTH response. The DTH test is considered positive if erythema and/or induration are recorded as positive on the DTH response electronic case report form (eCRF) page.
- Presence of TG02 specific T-cells in peripheral blood. A patient is considered to have a positive T-cell response if the stimulation index (SI) is ≥ 2 .

The SI will be derived as follows:

$$\frac{\text{Mean (T cells + PBMC + TG02)}}{\text{Mean (T cells + PBMC (negative control))}}$$

For SI, mean is derived as the sum of the non-missing measurements divided by the number of non-missing measurements, rounded to the nearest whole number.

- Change in intra-tumoural lymphocytes in resected tumour tissue at surgery compared to pre-TG02-treatment core biopsy will be investigated.

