6.1.1 TG02-specific DTH response

A TG02-specific DTH immune response is defined as any positive DTH test during the course of the study. A DTH-test will be considered positive if erythema and/or induration are recorded as positive on the DTH response assessment eCRF.

The number of positive DTH skin reactions (categorical variable) as well as the number and percentage of patients who have at least one positive DTH skin reactions will be presented by time point and overall.

All DTH assessment data will be listed in full.

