6.1.2 Presence of TG02-specific T-cells

Immunology-processed blood samples for peripheral blood mononuclear cells (PBMC) will be drawn at baseline and week 8 (Day 50). If surgery is after week 10, a third sample will be drawn as close as possible to the date of surgery. PBMCs will be analysed for the presence of TG02-specific T-cells. Summary statistics of patients with TG02-specific T-cells will be presented by time point and overall.

All PBMC and TG02-specific T-cell data will be listed.

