6.4.2 Handling of Dropouts or Missing Data

In general, the denominator for percentage calculations will be the number of patients in the analysis set. However, unless specified otherwise, for tables by time points the percentages and summary statistics will be calculated using the number of patients with available data at that time point.

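### Primary DTH, T-cell and immune response tables omit treated patients with neither surgery nor end biopsy; separately, the late by-visit rows (week 10 DTH, third PBMC sample) describe selected subgroups

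*SAP*

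**What the plan says.** **Analysis set.** SAP 4.2 defines the EAS as the set that "comprises all patients who undergo surgery after the treatment period or patients from whom a biopsy was obtained at the time of planned surgery". The per-protocol set (PPAS) is a subset of it. SAP 6 states: "All efficacy evaluations will be performed on the efficacy and per protocol analysis sets unless specified otherwise". The output table in SAP 4.2 agrees: the Immune Response row, the DTH row and the row that combines T-cell Responders with Biopsy are marked for EAS and PPAS, not for the safety set (SAF), which holds everyone who received any study product.

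**Endpoint.** SAP 6.1 defines a systemic immune response as "having a positive in vivo DTH and/or a positive in vitro T-cell response at least once during the study". Protocol 6.4.2 schedules DTH on Days 1, 22, 36 and 50 and PBMC samples on Days 1 and 50. SAP 6.1.2 adds a third PBMC sample only for surgery after week 10.

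**Patients outside the EAS.** Protocol 6.4 asks for an end biopsy in patients without surgery, but only where feasible. Protocol 7.5 gives as a withdrawal reason that "surgery does not proceed and the patient is unable or unwilling to provide a biopsy at the time of cancelled surgery". Protocol 7.6 says: "If a patient during the treatment period before surgery is withdrawn, the patient will be considered to be replaced". It states that safety data are kept in the analysis and is silent on immune data.

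**By-visit tables.** Under SAP 6.1.1, "the number and percentage of patients who have at least one positive DTH skin reactions will be presented by time point and overall". Under SAP 6.4.2, the general denominator is the analysis set, but for tables by time point "percentages and summary statistics will be calculated using the number of patients with available data at that time point". Neither section makes an exception for week 10.

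**The concern.** For intra-tumoural lymphocytes, requiring end tissue is sensible. For skin and blood endpoints it makes membership of the denominator depend on something that happens after most of the measurements. If the reasons for having neither surgery nor biopsy are related to immune response, the tabulated rate is selected. With 4-6 patients in Part I and up to 10 in Part II, one or two such patients move it visibly.

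The second issue is comparability across visits. Every version of the protocol rule gives the week 10 DTH test only to patients who are DTH-negative and have late surgery. A reader who sets the week 10 row beside weeks 4-8 compares different populations, and could take a low week 10 figure for waning while cumulative response is rising.

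**Working it through.** The plan gives no expected loss, response rate or formal sample size calculation, so there is no planned figure to reproduce. Apart from the Part sizes (SAP 3.4), all counts below are assumed.

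**1. Set membership.** A treated patient with neither surgery nor end biopsy is in SAF, not in EAS, and so not in PPAS. That patient is absent from all three tables even with DTH results from Day 1 to week 8.

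**2. Size.** Let N be treated, k outside the EAS and r the responders in the EAS. The EAS rate is r/(N - k). The all-treated rate lies between r/N and (r + k)/N, according to the unknown status of the k patients.

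| Case | N | k | r | EAS rate | All treated |
|---|---|---|---|---|---|
| Immune response | 10 | 2 | 5 | 5/8 = 62.5% | 5/10 to 7/10 = 50-70% |
| Immune response | 6 | 1 | 3 | 3/5 = 60% | 3/6 to 4/6 = 50-67% |
| T-cells | 10 | 2 | 4 | 4/8 = 50% | 4/10 to 6/10 = 40-60% |
| Nobody lost | N | 0 | r | r/N | r/N (identical) |

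The T-cell upper bound takes the SAP definition literally: a patient lost before Day 50 still has a Day 1 sample that could count.

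**3. One definition is needed.** As worded in SAP 6.1 and 6.1.1, a Day 1 positive counts. If 1 of the 4 EAS T-cell responders were positive on Day 1 only, the EAS rate would be 4/8 = 50% under that wording and 3/8 = 37.5% under a post-baseline rule. That is 12.5 points from the definition alone, so it must not differ between columns.

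**4. Week 10 DTH row.** Assume 10 patients, 6 positive at week 8 (row 60%) and 4 never positive.
- All 4 have late surgery and 1 converts: the week 10 row is 1/4 = 25%, while cumulative response is 7/10 = 70%.
- Only 2 of the 4 have late surgery: the row is 0/2, 1/2 or 2/2 = 0, 50 or 100%, with cumulative response 60, 70 or 80%.
- None has late surgery: there is no row.

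The overall ever-positive rate keeps its denominator of 10. However, the late-surgery negatives had one more chance to turn positive than the negatives operated on earlier. In this example that chance can move the overall rate from 60% to as much as 100% (4 tested, 4 converting).

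**5. Third PBMC sample.** It is limited to surgery after week 10, so its by-visit row is also a late-surgery subgroup, but it is not selected on an earlier result.

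**6. The protocol's week 10 DTH rules, side by side.**
- *Who:* no positive test so far (synopsis; 6.4.2; 9.1.1), or negative at week 8 (Figures 2 and 3, note 4; Table 6-1, footnote i; Table 8-1 footnote).
- *Surgery:* after week 10 (synopsis; 6.4.2; Table 6-1, footnote i; 9.1.1; Table 8-1 row label), or week 10 itself included (Figures 2 and 3, note 4; Table 8-1 footnote).
- *When:* Day 64 (6.4.2), or 48 hours before surgery (Table 6-1, footnote i). For surgery on Days 65-92 the latter is Day 65 - 2 = 63 to Day 92 - 2 = 90, up to 90 - 64 = 26 days later than Day 64.
- *Week 8 test:* listed in the synopsis, 6.4.2 and Tables 6-1 and 8-1, absent from 9.1.1.

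The *who* conflict changes the row. Assume 6 of 10 ever positive through week 8, of whom 2 are negative again at week 8 (row 4/10 = 40%). All 6 week 8 negatives have late surgery and 1 never-positive patient converts. The first rule gives 1/4 = 25%. The second gives (1 + b)/6 for b = 0, 1, 2 of the earlier positives testing positive again: 17, 33 or 50%. Cumulative response is 7/10 = 70% under both.

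**The case against.** Much is already in place. SAP 3.5 widened the protocol's surgery-only set to include patients with an end biopsy. SAP 4.1 tabulates how many patients are in each set and why patients withdrew, so a loss would be visible. SAP 4.2 lists all enrolled patients with the reason for exclusion, and with so few patients a reader can work through listings. Counts are required beside percentages (SAP 2), and the overall DTH rate is tabulated. The table shells are a separate document, so footnotes or n/N may already be planned there. No hypothesis is tested (SAP 6.4.1), and no document says how many patients will be lost.

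All of this stands and limits the consequence. It does not close the gap: the SAP 3.5 change helps only patients who give tissue, and a disposition count does not supply their DTH or T-cell results. It is also fair that a bare SAF percentage would count a patient withdrawn after Day 1 as a non-responder and so exchange one distortion for another. The remedy therefore has to name its denominators.

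Three stronger readings are tempting and not supported:
- *That the EAS inflates the response rate.* Direction is unknown; in each example above the EAS value lies inside the all-treated range.
- *That the decision on Part II rests on the selected set.* SAP 3.2 bases the committee's recommendation on data from all Part I patients.
- *That the week 10 rule invalidates the overall DTH rate.* Its denominator is fixed; the chance of being found positive is unequal.

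**Conclusion.** The point holds on both counts and should be corrected before database lock, although it does not threaten the study's conclusions.

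(1) The three primary skin and blood tables exclude treated patients with neither surgery nor end biopsy, for no reason that these endpoints require. The effect is zero if nobody is lost. With 2 of 10 lost and 5 EAS responders, 62.5% is reported where the all-treated rate could be anywhere from 50 to 70%. These are illustrations, since the number lost and their results are unknown, and the rate may move either way.

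(2) The week 10 DTH row is a rate in a DTH-negative, late-surgery subgroup and is not comparable with weeks 4-8. The third PBMC row is a late-surgery subgroup. This is mainly a matter of presentation, except that the protocol's conflicting week 10 rules leave the population and timing of the row undefined.

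**What to change.** **SAP 4.2 table.** Split T-cell Responders from Biopsy. Add SAF to the Immune Response, DTH and T-cell rows, including replaced patients. Report two rates with both Ns shown:
- responders over all SAF patients, with untested patients counted as non-responders and labelled so;
- responders over patients with at least one post-baseline result for that endpoint.

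Use one response definition in SAF, EAS and PPAS. If a post-baseline definition is preferred to the present wording, state it as a change and apply it to every set. Keep EAS and PPAS for tissue endpoints, and alongside SAF for these.

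**SAP 6.1.1 and 6.1.2.** Show week 10 DTH and the third PBMC sample as n/N tested, with a footnote on how those patients were selected. Add a cumulative ever-positive DTH row by visit over the fixed analysis-set denominator.

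**Protocol.** Reconcile the synopsis, Figures 2 and 3 (note 4), 6.4.2, Table 6-1 (footnote i), Table 8-1 and 9.1.1 on who has the week 10 DTH test, when it is done and whether a week 8 test precedes it. Until then the row should not be labelled as conversion among prior negatives.

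**Cost.** No new data: SAP wording, a few columns, footnotes and one row, plus the protocol clarification. SAP 1 already provides for revision before lock, and if SAF equals EAS the SAP does not repeat outputs.
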